## Statistical Analysis Plan

Patients erroneously enrolled in the study (i.e., not fulfilling the eligibility criteria) will be excluded from all analyses of this study and any deviations from the protocol will be reported in detail in the clinical study report (CSR).

### 3.6 Coding dictionaries

#### MedDRA dictionary

The Medical Dictionary for Regulatory Activities (MedDRA) (*the last updated version available at the onset of medical coding*) will be used for the coding of the verbatim terms of significant medical history/comorbidities and reported AEs.

Recorded terms will be coded according to Lower Level Term (LLT), Preferred Term (PT) and System Organ Class (SOC) and will be presented by PT and SOC.

#### WHOCC-ATC classification dictionary

Concomitant and prior treatment for NSCLC will be coded using the Anatomical Therapeutic Chemical (ATC) controlled by the World Health Organization (WHO) Collaborating Centre for Drug Statistics Methodology (WHOCC).

In particular, recorded prior treatment for NSCLC will be presented in the categories pre-specified in the eCRF (i.e. surgical procedures, radiotherapy, systemic chemotherapy), while all other medications recorded in the field 'other' will be coded by the WHOCC ATC in terms of chemical subgroup (4th level) and chemical substance (5th level). Concomitant treatment for NSCLC will be presented as radiotherapy (predefined option in the eCRF), while medications will be coded according to the WHOCC ATC, therapeutic subgroup (2nd level), chemical subgroup (4th level) and chemical substance (5th level), as applicable.

### 3.7 Definitions of study-specific derived variables

#### 3.7.1 Derived variables

- ✓ Age at enrolment

Age at enrolment (years) = (Date of enrolment - Date of birth)/365.25.

- ✓ BMI (kg/m^2) = Weight (Kg) / Height (m)

*BMI (kg/m^2) will be calculated at the enrolment visit and at the post-baseline time points.*

- ✓ BMI (kg/m^2) classification:

- *Underweight (BMI < 18.5 Kg/m^2);*
- *Normal (18.5 Kg/m^2 ≤ BMI < 25 Kg/m^2);*
- *Overweight (25 Kg/m^2 ≤ BMI < 30 Kg/m^2);*
- *Obese (BMI ≥ 30 Kg/m^2).*

- ✓ Pack-years of smoking

## Statistical Analysis Plan

$$\text{Pack-years of smoking} = \frac{\text{Average number of cigarettes/day} \times \text{Years of smoking}}{20}.$$

- ✓ Age at initial diagnosis of NSCLC

Age at initial diagnosis of NSCLC (years) = (Date of initial diagnosis of NSCLC – Date of birth)/365.25.

- ✓ Age at diagnosis of locally advanced/metastatic NSCLC

Age at diagnosis of locally advanced/metastatic NSCLC (years) = (Date of diagnosis of locally advanced/metastatic NSCLC – Date of birth)/365.25.

- ✓ Time elapsed from initial diagnosis of NSCLC to locally advanced /metastatic NSCLC

Time elapsed from initial diagnosis of NSCLC to locally advanced /metastatic NSCLC (months) = (Date of diagnosis of locally advanced/metastatic NSCLC - Date of initial diagnosis of NSCLC)/30.5.

- ✓ Time elapsed from diagnosis of locally advanced/metastatic NSCLC to enrolment

Time elapsed from diagnosis of locally advanced/metastatic NSCLC to enrolment (months) = (Date of enrolment – Date of diagnosis of locally advanced/metastatic NSCLC)/30.5.

- ✓ Age at afatinib treatment onset

Age at afatinib treatment onset (years) = (Date of afatinib treatment onset - Date of birth)/365.25.

- ✓ Time elapsed from afatinib treatment onset to enrolment

Time elapsed from afatinib treatment onset to enrolment (days) = (Date of enrolment – Date of afatinib treatment onset).

- ✓ Time elapsed from the diagnosis of locally advanced/metastatic NSCLC to afatinib treatment onset

Time elapsed from the diagnosis of locally advanced/metastatic NSCLC to afatinib treatment onset (months) = (Date of afatinib treatment onset - Date of diagnosis of locally advanced/metastatic NSCLC)/30.5.

- ✓ Duration of afatinib treatment

Duration of afatinib treatment (months) = (Date of afatinib discontinuation – Date of afatinib treatment onset+1)/30.5; *for patients who discontinued afatinib treatment*

or

Duration on afatinib treatment (months) = (End date of study participation – Date of afatinib treatment onset+1)/30.5; *for patients who did not discontinue afatinib treatment.*

## Statistical Analysis Plan

### 3.7.2 Patient Reported Outcomes

In regards to PROs the scoring instructions provided from the Sponsor will be followed.

- ✓ *Total LCSS score & ASBI score*

The patient-rated LCSS scale consists of six symptom-specific questions that address loss of appetite, fatigue, cough, dyspnoea, pain and haemoptysis, as well as three global items overall symptomatic distress, interference with normal activity, global Quality of Life (QoL). Each item is scored on a 100-mm VAS, with score reported from 0 to 100 with 0 representing the best score.

- *Total LCSS score will be calculated by the mean of the 9 items of the scale. For a given assessment, if any of the nine items have not been completed, the total LCSS score will not be calculated.*
- *ASBI score will be calculated by the mean of the 6 major lung cancer symptoms (loss of appetite, fatigue, cough, dyspnoea, pain and haemoptysis). For a given assessment, if any of the six symptom-specific questions have not been completed, the ASBI score will not be calculated.*

- ✓ *EQ-5D utility index score*

The EQ-5D-3L descriptive system consists of the following 5 dimensions: *mobility, self-care, usual activities, pain/discomfort and anxiety/depression*. Each dimension has 3 levels: 1=“no problems”; 2=“some problems”; 3=“extreme problems” (which have no arithmetic properties and are not used as a cardinal score [EuroQol Group 1990^18; Rabin and de Charro 2001]).

For the calculation of the EQ-5D utility index score based on the patients’ responses to the 5 dimensions, each patient’s responses will be assigned to a health state. The specific EQ-5D index score assigned to each health state will be based on value sets provided by the Sponsor.

### 3.8 Changes from planned analyses

No change from the planned analysis has been conducted.

## 4 STATISTICAL/ANALYTICAL ISSUES

### 4.1 Adjustments for covariates

The following variables will be considered as potential confounders or effect modifiers of the impact of treatment with afatinib on the improvement in disease-specific symptom burden.

- ✓ Age at baseline;
- ✓ Gender;
- ✓ BMI at baseline;
- ✓ Educational/marital/employment status;
- ✓ Baseline comorbidity count with particular emphasis on gastrointestinal, psychiatric, and musculoskeletal and connective tissue disorders;

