### **11.8.2 Analysis for the primary endpoint**

Pertaining to the primary endpoint the proportion of patients experiencing a minimum clinically important symptom improvement (*as defined in Section 11.1.3.1*) over a 6-month period of treatment will be calculated along with the respective 95% confidence interval; in addition the relevant proportions of patients whose symptom burden has remained stable and deteriorated will be calculated. The 95% confidence interval will be derived from Wald confidence limits for a binomial proportion.

In order to examine the impact of baseline characteristics including among others, gender, age, BMI, educational/marital/employment status, disease stage, histological subtype, sites of metastases, EGFR mutation subtype, smoking status and smoking history, ECOG PS, type of concomitant medications and comorbidities, as well as adherence to therapy at 6 months on the study primary endpoint, a binary logistic regression model will be applied.

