## Statistical Analysis Plan

### 2.1 Study objectives and endpoints

#### 2.1.1 Primary objective and endpoint

The primary objective of the study is:

- To evaluate the impact of afatinib therapy on the patient-reported lung cancer-specific symptom burden, using the Average Symptom Burden Index (ASBI) of LCSS in eligible patients, over 6 months of therapy, in a real world clinical setting in Greece.

The primary endpoint of the present study is:

- 6-month symptom improvement rate using the LCSS ASBI, i.e., proportion of patients who will experience a minimum clinically important improvement in symptoms (defined as a decrease in the ASBI from enrolment  $\geq 10$  in two consecutive assessments) over 6 months of treatment.

*Note: A patient will be categorized as having:*

- ✓ *an improved ASBI if the mean of any two consecutive post-baseline ASBI assessments for that patient is at least 10 points below the patient's ASBI at enrolment;*
- ✓ *a worsened ASBI if the mean of any two consecutive post-baseline ASBI assessments for that patient is at least 10 points above the value at enrolment;*
- ✓ *a stable ASBI if the mean of any two consecutive post-baseline ASBI assessments for that patient is within 10 points of the value at enrolment.*

*A change of 10 points on a 0-100 scale is considered sufficient to indicate a clinically meaningful change; this magnitude is about the same as the 0.5 standard deviation that has also reported as a universally acceptable minimum clinically important difference.*

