## Statistical Analysis Plan

- ✓ Histologically or cytologically confirmed locally advanced or metastatic (IIIB/IV) NSCLC of any histological type with activating EGFR mutation(s) according to local laboratory EGFR testing;
- ✓ EGFR-TKI naïve patients;
- ✓ Patients for whom the decision to prescribe therapy with afatinib (GIOTRIF®) according to the locally approved product's SmPC has already been taken prior to their enrolment in the study and is clearly separated from the physician's decision to include the patient in the current study;
- ✓ Patients must be able and willing to provide written informed consent and to comply with the requirements of this study protocol;
- ✓ Patients must have signed an informed consent document;
- ✓ Patients must be able to read, understand and complete the study specific questionnaires.

A patient who meets **any** of the following criteria will be excluded from participation in this study:

- ✓ Patients who have initiated treatment with afatinib more than 7 days prior to their enrolment into the study;
- ✓ Patients that meet any of the contraindications to the administration of the study drug according to the approved SmPC;
- ✓ Patients currently receive treatment with any investigational drug/device/intervention or have received any investigational product within 1 month or 5 half-lives of the investigational agent (whichever is longer) before the commencement of therapy with afatinib.

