### 3.5 Analysis sets

In accordance to the non-interventional design of the study, all statistical analyses will be performed in the Full Analysis Set (FAS) comprised of all eligible subjects who have been enrolled in the study, regardless of whether or not they have finally completed their projected participation in the study.

The analysis of the primary objective of the study will be performed in the Per Protocol Set (PPS) which will include all eligible study patients with available data pertaining to the study primary endpoint, i.e. 6-month symptom improvement rate as per the LCSS ASBI score. In case that the size of the PPS differs substantially (i.e.  $\geq 20\%$ ) from the size of the FAS, then descriptive statistics of demographic and baseline disease and clinical characteristics will also be presented in the PPS.

Subsets of FAS with available data will also be created and analysed for the purposes of secondary endpoint analyses. The safety analysis will also be applied in the FAS.

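### Enrolment ASBI is not among the listed covariates for the primary endpoint, and patients who enrol below 10 points are counted in the rate although they cannot meet the 10-point fall

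*SAP*

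**What the plan says.** - **Endpoint (SAP 2.1.1, Protocol 11.1.3.1).** A patient is improved if "the mean of any two consecutive post-baseline ASBI assessments for that patient is at least 10 points below the patient's ASBI at enrolment".
- **Scale (SAP 3.7.2).** "Each item is scored on a 100-mm VAS, with score reported from 0 to 100 with 0 representing the best score". ASBI is the mean of six such items, so its floor is also 0.
- **Eligibility (SAP 3.4).** The only criterion that concerns the questionnaires is "Patients must be able to read, understand and complete the study specific questionnaires". There is no minimum symptom score.
- **Denominator (SAP 3.5).** The primary analysis uses the PPS, "which will include all eligible study patients with available data pertaining to the study primary endpoint". It has no condition on enrolment ASBI.
- **Covariates.** SAP 4.1 begins "The following variables will be considered as potential confounders or effect modifiers of the impact of treatment with afatinib" and lists age, gender, BMI, social status, comorbidity, concomitant medication, stage, ECOG PS, smoking, histology, EGFR subtype, metastases and adherence. Protocol 11.4.4 gives the same set.
- **Model (Protocol 11.8.2).** "In order to examine the impact of baseline characteristics including among others, gender, age, BMI" and further factors on the primary endpoint, "a binary logistic regression model will be applied". Enrolment ASBI is not among those named.

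**The concern.** The score from which the endpoint is calculated is collected at enrolment for the primary endpoint, yet no visible covariate list names it. Two consequences follow.

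First, some patients are not improved by arithmetic, whatever the drug does. The study has no control group, so readers will take the improvement rate at face value. They need to know how much of the non-improved group could never have improved.

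Second, the logistic model is the planned way to describe who improves. A factor that goes with a higher enrolment score, such as worse ECOG PS, can look like a predictor of improvement for two reasons. Fewer of those patients sit near the floor, and unusually high enrolment scores tend to fall back.

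**Working it through.** **1. The plan's own figure.** The inputs from SAP 2.4 are p = 0.50, margin d = 0.10 and 95% confidence.
- n = 1.96² × 0.50 × 0.50 / 0.10² = 96.04, against 96 stated.
- Relative standard error = √(0.25/96) / 0.50 = 10.21%, as stated.
- Enrolled = 96 / 0.75 = 128, as stated.

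The figures reproduce. Because p = 0.50 gives the widest Wald interval, a rate pulled below 0.50 by the floor still meets the margin with 96 patients.

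**2. The floor.** Improvement needs a two-visit mean of at most (enrolment ASBI − 10). If enrolment ASBI is below 10, that limit is negative and cannot be reached. With f the share who enrol below 10:

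overall rate = (1 − f) × rate in patients at 10 or more, so the maximum is 1 − f.

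**3. How large f might be.** The documents give no enrolment distribution. SAP 2.1.1 equates 10 points with about half a standard deviation, which implies an SD near 20. The means are assumptions. For a normal score, f = Φ((10 − mean)/20).

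**4. What the floor costs.** I simulated scores at enrolment and at months 2, 4 and 6 as normal with SD 20, a true fall of 8 points and between-visit correlation 0.5 to 0.7. I applied the endpoint rule with and without limiting scores to 0–100.

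| Mean enrolment ASBI | f | Rate, no floor | Rate, with floor | Cost of floor (points) | Rate at 10 or more, with floor |
|---|---|---|---|---|---|
| 25 | 22.7% | 53–55% | 45–48% | 6.8–7.8 | 59–62% |
| 30 | 15.9% | 53–55% | 48–50% | 4.4–5.1 | 57–60% |
| 35 | 10.6% | 53–55% | 50–52% | 2.6–3.1 | 56–58% |
| 40 | 6.7% | 53–55% | 52–53% | 1.4–1.8 | 55–57% |

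The share below 10 is sensitive to the assumed shape. A beta distribution with SD 20 gives 29% at mean 25 and 5% at mean 40. With SD 15 it gives 16% and 1%.

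**5. Floor or regression to the mean?** For means 25 to 35, improvement by enrolment score is:

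| Enrolment ASBI | With floor | Without floor |
|---|---|---|
| below 10 | 0% | 14–28% |
| 10–25 | 27–41% | 32–47% |
| 25–45 | 53–68% | 54–68% |
| 45 or more | 74–89% | 75–89% |

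Above 25 the floor makes almost no difference. Most of the gradient is regression to the mean.

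**6. Effect on odds ratios.** Two simulated factors, each present in 30% of patients and neither affecting the true change:
- *Enrolment score without noise; factor raises it by 10–15 points.* At mean 20, 30 and 40 the factor's odds ratio is 1.7–2.1, 1.3–1.5 and 1.1–1.2 without enrolment ASBI in the model. With it, the odds ratio is 1.14–1.19, 1.03–1.05 and 0.99–1.01. Adjustment removes most of the artefact.
- *Noisy enrolment score (correlation 0.6); factor raises every visit by 12 points.* At means 25 to 40 the odds ratio is 1.07–1.29 unadjusted and about 0.52 adjusted. Adjustment here creates an apparent effect in the opposite direction.

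**7. Precision of a supportive rate.** At f = 7%, n = 96 × 0.93 = 89.3 and the half-width is 1.96 × √(0.25/89.3) = 0.104. At f = 23%, n = 96 × 0.77 = 73.9 and the half-width is 0.114.

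**The case against.** Several stronger readings are tempting, and the documents do not support them.

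- **That the primary model omits enrolment ASBI.** This is not shown. SAP 4.1 lists variables to consider and is not a model specification. The protocol's list for the logistic model is explicitly open. The SAP refers to Sections 8.1.3 and 8.2, but the public copy passes from Section 7 to Section 9, so the model text cannot be read. Only 'not listed' can be said.
- **That the primary rate is biased.** It is a valid estimate of a proportion defined over all evaluable patients, in a descriptive study without a hypothesis. Dependence on case mix is inherent in a single-arm rate.
- **That the gap between all patients and those at 10 or more is the floor's cost.** For means 25 to 35 that gap is about 6 to 14 points, but the floor accounts for only about 2.5 to 8. The restricted rate exceeds even the no-floor rate, because selecting on a high enrolment score brings in regression to the mean. Nor is the plan's 0.10 margin a yardstick here, since it measures sampling precision.
- **That the adjusted model is the correct one.** Step 6 shows that it can reverse a sign.

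The plan also softens the problem. Stable and worsened proportions are reported, so a patient with few symptoms can appear as stable. Change in ASBI is also analysed as a continuous score, without the 10-point threshold. All of this stands. It limits the size of the point, but does not tell readers how many patients could not improve, nor help them interpret the regression.

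**Conclusion.** The point holds as a matter of interpretation and pre-specification. Enrolment ASBI is named in no visible covariate list, and a patient who enrols below 10 counts in the PPS without being able to improve. That much is certain from the documents. The size is not: assuming SD 20, mean 25 to 40 and a true fall of 8 points, about 7 to 23% start below 10 and the floor takes about 1.5 to 8 points off the all-patient rate. Odds ratios for factors linked to baseline symptoms partly reflect room to improve and regression to the mean. The primary estimate is not invalid, and the 96 evaluable and 128 enrolled patients are unaffected. This is a cheap improvement, not a correction of an error in the primary analysis.

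**What to change.** Keep the all-patient rate as primary, and add to the SAP:

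1. The number and percentage of patients with enrolment ASBI below 10.
2. A supportive improvement rate with 95% CI in patients with enrolment ASBI of 10 or more, with a note that its interval is wider and that selecting on a high enrolment score raises the rate through regression to the mean.
3. Enrolment ASBI in Section 4.1, allowing non-linearity, as a sensitivity version of the logistic model, shown beside the model without it. State that the adjusted odds ratios are conditional on a noisy enrolment score and can shift or reverse, so that neither version is read alone.

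The cost is some SAP wording and a little extra tabulation. No new data are needed, because the enrolment score is already collected. If unpublished Section 8 already names enrolment ASBI, item 3 reduces to aligning Section 4.1 with it and showing both models.

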## Statistical Analysis Plan

- ✓ Concomitant medications both at baseline and at the time of symptom burden assessment with particular emphasis among others on analgesics, antitussives, antidepressants, antiemetics, and antidiarrheals;
- ✓ Disease stage at baseline;
- ✓ Baseline ECOG PS;
- ✓ Baseline smoking status and lifetime tobacco exposure;
- ✓ Lung cancer histologic classification;
- ✓ EGFR mutation subtype;
- ✓ Sites of metastases at baseline;
- ✓ Adherence to afatinib treatment over the 6-month observation period and over the whole study participation duration.

### 4.2 Handling of dropouts or missing data

With regard to partial start dates with a missing start day, e.g. \_ \_ JUN2016, the day will be set to the first of the month, 01JUN2016. If the month is missing e.g. 17 \_ \_ 2016, the month will be set to January for that year, 17JAN2016. The reverse will apply for a partial end date, with the missing day set to the end of the month and the missing month set to December. If there is only a year and both the day and month are missing, then both are imputed, giving 1st January for a start date or 31st December for a stop date. In case where a partial date after the general imputation rule comes in reasonable opposition with another variable of the eCRF, then the date will be imputed so as to be in reasonable time sequence.

In the context of the final analysis, regarding the primary outcome measure, in case of a high non-evaluable rate (i.e. >20%) the primary endpoint analysis will also be conducted in the subset of patients with at least one post-baseline measurement of the ASBI score. Details about this analysis are presented in Section 8.1.3.

### 4.3 Interim analyses

Taking into consideration the long-term study duration as well as the current limited evidence on the real-world clinical outcomes of treatment with afatinib in patients with NSCLC, an interim analysis is planned to be performed after the first 40 enrolled patients (i.e., around one-third of the overall sample size) have completed the 6-month study observation period (i.e., have attended the 6-month study visit [V4] or have discontinued study participation, whichever occurs first).

The main purpose of the interim analysis is to gain preliminary information on the impact of afatinib in the study key outcome measures. No resultant decisions and actions will be taken in terms of the study progress as a consequence of the interim analysis. The interim analysis does not involve any stopping boundary for early stop due to efficacy or for sample size adjustment, thus no multiplicity adjustment will be performed.

## **Statistical Analysis Plan**

In the context of the interim analysis, taking into consideration that the sample size of this analysis will be 40 patients (around one-third of the overall sample size) and aiming to ensure the scientific validity of the results, the missing rate of the primary and key secondary outcomes (i.e. symptoms improvement, LCSS score, EQ-5D, and ECOG) will be calculated and each of the respective analyses will be performed only in those cases that the missing data rate does not exceed 20%.

Only descriptive statistical measures and epidemiological methods will be applied for the purposes of the interim analysis. Continuous variables will be summarized with the use of descriptive statistical measures ( $n_{pt}$ ,  $n_{miss}$ , mean, SD, median, 25th and 75th percentiles and range) and categorical variables will be presented with the use of frequency tables ( $n_{pt}$ , %). All the analyses will be conducted providing that the number of patients included in each analysis will allow for meaningful inferences.

### **4.4        Multiple comparisons/multiplicity**

No formal multiple comparisons between specific subgroups of patients have been foreseen and therefore statistical adjustment does not fall within the scope of this analysis, while control of type I error is not required.

